7 EVALUATION CRITERIA

An overview of the imaging trial criteria evaluated by the investigator (INV) and the Independent Blinded Readers (IBR) is provided in the [Table 2](#) below:

Table 2: Overview of imaging trial criteria

Images	Pre gadopiclenol	Pre gadobutrol	Paired gadopiclenol	Paired gadobutrol	Global matched-pairs
Lesion visualization	INV/IBR	INV/IBR	INV/IBR	INV/IBR	
Technical adequacy of images	INV/IBR	INV/IBR	INV/IBR	INV/IBR	
Number, size and location of lesions	INV/IBR	INV/IBR	INV/IBR	INV/IBR	
Diagnostic confidence	INV/IBR	INV/IBR	INV/IBR	INV/IBR	
Impact of contrast-enhanced MRI on patient treatment plan			INV	INV	
Percentage enhancement (E%) of lesion			IBR	IBR	
Lesion to Background Ratio (LBR)			IBR	IBR	
Overall diagnostic preference					IBR

INV: Investigator (on-site)

IBR: Independent Blinded Readers (off-site)

The image sets evaluated per patient are described in the [Table 3](#) below:

Table 3: Images sets per patient

Image Set Number	Type
1a	Pre images = unenhanced MRI before gadopiclenol injection
2a	Pre images = unenhanced MRI before gadobutrol injection
1b	Paired images = combined unenhanced and gadopiclenol-enhanced MRI (pre+post images)
2b	Paired images = combined unenhanced and gadobutrol-enhanced MRI (pre+post images)

 CONFIDENTIAL	Protocol No. GDX-44-011 Version No. 3.0 (including amendment 2) June 30, 2020	Page 38 / 82
---	---	--------------

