- 3 = Injection technical failure
- 4 = Inadequate anatomic coverage
- 5 = Other, specify

7.2.6 ***Number, size and location of lesions (on-site and off-site read)***

The investigator and IBR is to record the following:

- Number of lesions on pre and paired images
- For the most 3 representative lesions, the following will be recorded for each lesion separately:
 - The largest diameter of the lesion
 - The location of the lesion
- In case that more than 3 lesions are present, the investigator/IBR has to enter in the eCRF how many lesions are present (total number).

 CONFIDENTIAL	Protocol No. GDX-44-011 Version No. 3.0 (including amendment 2) June 30, 2020	Page 41 / 82
---	---	--------------

7.2.7 ***Diagnostic confidence (on-site and off-site read)***

The investigator/IBR will record in the eCRF his/her diagnosis and his/her confidence in diagnosis for each patient for each pre and paired images of each contrast agent according to the following diagnosis:

- 1 = Negative
- 2 = Benign
- 3 = Probably Benign finding
- 4A = Low Suspicion of Malignancy
- 4B = Intermediate Suspicion of Malignancy
- 4C = Moderately High Suspicion of Malignancy
- 5 = Not assessable

If malignancy is diagnosed, then whether the tumor is primary or secondary should be specified.

Diagnostic confidence will be evaluated to determine the level of certainty that the investigator/IBR assign to a diagnosis. This is defined as the degree of confidence that the information on the images represents the true and complete clinical picture of a patient.

The degree of confidence will be rated on a 5-point scale:

- 1 = Nil: very uncertain
- 2 = Poor: uncertain
- 3 = Moderate: moderately certain
- 4 = High: good certainty
- 5 = Excellent: very certain

When the investigator/IBR chooses 'not assessable' for diagnosis, by definition the confidence level is 1 (= very uncertain).

7.2.8 ***Impact of contrast-enhanced MRI on patient treatment plan (on site)***

The impact on patient treatment plan will be assessed by on-site radiologists and will be summarized for each contrast agent. At the end of visit 2 and at the end of visit 4, after having completed all the sequences of images required by the protocol (images set 1b or set 2b), the investigator will have to document if the patient treatment plan could have been changed based on the images obtained (yes/no) and if yes, he/she would have to specify the therapeutic management proposed based on radiological assessment:

- Surgery
- Biopsy

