The patients within each batch will be ordered at random without stratification into groups of patients.

Various modalities of images from the same patient will not be presented in the same batch and the Imaging Core Laboratory will ensure an appropriate wash-out period between the evaluations of images

 CONFIDENTIAL	Protocol No. GDX-44-011 Version No. 3.0 (including amendment 2) June 30, 2020	Page 51 / 82
--	---	--------------

from two modalities (Pre and Paired images) and between two MR examinations for the same patient, to minimize recall bias.

8.4.7 ***Blinded Assessment of Images***

Imaging database including all evaluable images will be assessed by the independent readers. The reading will be performed in a strictly fully blinded manner.

No communication on patient specific image findings will be allowed between the independent readers once the blinded reviews begin.

To ensure that the centralized reading evaluations remain independent, each individual reader evaluation will be locked as they occur (i.e., it will not be possible to alter the evaluation).

8.4.8 ***Inter and Intra-reader Variability Assessment***

The assessments of inter- and intra-reader variability will be done in the final analysis.

Inter-reader variability will be evaluated on the whole set of trial patients, since each patient will be read by different readers.

Intra-reader variability: individual readers will perform repeat image evaluations of 10% of cases randomly determined. The cases used for intra-reader variability assessment will be re-introduced randomly and re-read during the course of the reading. To minimize recall bias, intra-reader variability will be assessed approximately after the first 50 cases are reviewed and no sooner than two weeks from the original reviews of these patients. Results of the original reviews for these cases will not be available to the reader. Only the first evaluation of a given image set will be included in the efficacy analysis.

8.4.9 ***Lesion tracking/Matching***

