The lesion visualization criteria and the mean score calculation are presented in [section 2.2.1](#). For each contrast agent and for the 3 co-primary criteria, the mean score is calculated and compared between Pre contrast and Paired images. If the mean score in Paired images is greater than in Pre contrast images then the Paired image will be classified as “Better”. If the mean score in Paired images is equal or less than in Pre contrast images then the Paired image will be classified as “Not Better”.

- Technical adequacy of images (on-site and off-site read)

For each contrast agent, images will be evaluated as technically adequate for diagnosis and as assessable or not by investigators and IBR.

The technical adequacy of images will be rated on a 4-point scale:

- 1 = Non diagnostic
- 2 = Poor
- 3 = Fair
- 4 = Good

Images should be evaluated as assessable or not and if not, the reasons should be recorded:

- 1 = Artifacts due to patient
- 2 = Artifacts due to machine
- 3 = Injection technical failure
- 4 = Inadequate anatomic coverage
- 5 = Other, specify

- Number, size and location of lesions (on-site and off-site read)

Number and location of lesions is assessed for each contrast agent on Pre contrast and Paired images.

The size (largest diameter) of the 3 most representative lesion will be recorded.

- Diagnostic confidence (on-site and off-site read)

The investigator/IBR will record in the eCRF his/her diagnosis (Malignant lesion, yes, no or not assessable) and his/her confidence in diagnosis for Pre contrast and Paired images of each contrast agent

Degree of confidence for each contrast agent will be assessed using a 5 point-scale

- 1 = nil: very uncertain
- 2 = poor: uncertain
- 3 = moderate: moderately certain
- 4 = high: good certainty
- 5 = excellent: very certain

- Impact of contrast-enhanced MRI on patient treatment plan (on site)

The impact of contrast-enhanced MRI on patient treatment plan is assessed for each contrast agent by whether the patient treatment plan has changed based on the images obtained (yes/no). If yes, the therapeutic management proposed based on radiological assessment is the following:

- Surgery
- Biopsy
- Chemotherapy
- Radiotherapy
- Other treatment: specify

The 2 quantitative criteria (E% and LBR) will be calculated in averaging the parameter for maximum 3 most representative lesions for each contrast agent (off-site read).

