## Lesion size analysis for lesion visualization at lesion level (off site read)

Lesion visualization at lesion level (off site read) analysis comparing the two GBCA will be repeated with size of lesion added as co-factor. Size will be classified as following:

- $=<1$  cm
- $>1$  cm and  $=<2$  cm
- $>2$  cm

Hence the models will be the following:

- Border delineation = contrast agent group + period + reader + center + class\_size + error
- Internal morphology = contrast agent group + period + reader + center + class\_size + error
- Degree of contrast enhancement = contrast agent group + period + reader + center + class\_size + error

The parameters of the general linear model will be estimated using the SAS® procedure Mixed. The procedure used for the analysis will be the following, for each criterion:

```

proc mixed data = XXX method = REML;
  class lesion_# GBCA period reader center class_sized;
  model eval = GBCA period reader center class_sized;
  repeated GBCA / subject=lesion_# / type = cs;
/* To get the estimate and the corresponding confidence interval of the paired difference */
  lsmeans GBCA;
  lsmeans GBCA* class_sized
  estimate "gadopiclenol - gadobutrol" GBCA 1 -1 /cl;
  estimate "gadopiclenol - gadobutrol" GBCA* class_sized ... /cl;
run;

```

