### **Size of lesions**

The size (largest diameter) of the 3 most representative lesions will be assessed by off-site readers and on-site radiologists and will be summarized by contrast agent groups and MRI modalities (pre and paired) ; off-site and on-site reader's outcomes will be separately analyzed.

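### The SAP's lesion-size analysis does not say which diameter defines the size class, so one lesion can fall in different classes for the two agents and the size-adjusted agent difference can be biased

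*Protocol*

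**What the plan says.** **How diameter is collected.** Protocol 7.2.6 tells the investigator and each off-site reader: "For the most 3 representative lesions, the following will be recorded for each lesion separately". The items listed are the largest diameter and the location. In Protocol Table 2, the row "Number, size and location of lesions" is marked for investigator and blinded readers in all four columns: Pre and Paired, for each agent. Protocol 8.4.6 keeps these reads apart: "Various modalities of images from the same patient will not be presented in the same batch". It also requires a wash-out between the two examinations.

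**Diameter as an outcome.** SAP 2.2.2 lists it among the secondary efficacy criteria: "The size (largest diameter) of the 3 most representative lesion will be recorded". Under SAP 5.6.2, Size of lesions, it "will be summarized by contrast agent groups and MRI modalities (pre and paired").

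**Diameter as a covariate.** In the lesion-size analysis of SAP 5.6.2, the lesion-level "analysis comparing the two GBCA will be repeated with size of lesion added as co-factor". The classes are up to 1 cm, over 1 to 2 cm, and over 2 cm. The code has one record per lesion and agent (REPEATED with the lesion as subject, compound symmetry). Its model line is "model eval = GBCA period reader center class_sized". It then asks for "lsmeans GBCA* class_sized" and for agent differences within size class. The parent lesion-level analysis keeps both matching and non-matching lesions.

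No section says whether the class comes from the Pre or the Paired images, from which agent's examination, or from an average.

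**The concern.** A stratifying variable in a within-lesion comparison of two agents should be a property of the lesion, not of the agent. Here the only sizes in the data are readings per image set. A programmer working from the SAP would most naturally attach to each row the diameter read on the images that gave that row's score. Two things follow.

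- The model conditions on a quantity measured after injection that the plan itself treats as an outcome. Protocol 7.1.1 defines border delineation to include detecting the extent of the lesion, so an agent that shows extent better could change both the score and the diameter.
- A lesion near 1 cm or 2 cm can be in one class for gadopiclenol and another for gadobutrol. If one agent reads larger, its borderline lesions move up a class. Each of its classes then holds lesions that are truly a little smaller than those in the other agent's class. If smaller lesions score lower, that agent's mean falls in every class, although no lesion is scored worse. This is stage migration.

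At stake is any statement about small lesions, or about the agent comparison after allowing for size, drawn from Tables 14.2.2.16 and 14.2.2.17.

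**Working it through.** The plan gives no sample size, power or margin for this analysis, so there is no planned figure to reproduce. The check asks what happens if each row carries its own Paired diameter.

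**Inputs.** From the SAP: cut-points at 10 and 20 mm, one row per lesion and agent, compound symmetry, score scale 1 to 4. Everything else is assumed, because the documents give no diameter distribution, reading error, agent effect on diameter or relation of score to size.

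**Scale of the effect.** Let the score rise by s per log unit of diameter and let one agent's diameters read r times larger. At equal measured size, that agent's lesions are truly smaller by ln(r) in log size, so its mean is shifted by about -s × ln(r). With s = 0.5:
- r = 1.05: -0.5 × 0.0488 = -0.024
- r = 1.10: -0.5 × 0.0953 = -0.048

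Three coarse classes remove only part of the size information, so somewhat smaller values are expected.

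**Simulation A.** 1,000,000 matched lesions per scenario; lognormal diameters with median 12 or 18 mm and log-SD 0.6; reading error 8 to 15%; s = 0.5; true agent difference 0.

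| Diameter ratio | Lesions in discordant classes | Difference within class, own-row class | Difference within class, one common class |
|---|---|---|---|
| 1.00 | about 10 to 18% | 0 within simulation error | 0 within simulation error |
| 1.05 | about 10 to 19% | about -0.01 to -0.02 | 0 within simulation error |
| 1.10 | about 12 to 20% | about -0.03 to -0.04 | 0 within simulation error |

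The main-effects model as coded, fitted by generalised least squares with own-row class (median 18 mm, error 10%), gives an overall agent effect of about -0.02 at ratio 1.05 and -0.03 at 1.10, where the truth is 0. The overall size-adjusted difference is therefore exposed, not only the class-specific ones. The common class here is the class of the mean of the two Paired diameters.

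**Simulation B, different assumptions.** 400,000 lesions per scenario; median 15 mm, log-SD 0.6; additive reading error SD 1, 2 or 3 mm; score slope 0 or 0.3 per doubling of diameter; true difference 0.10 in every class.

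- No agent shift: 9%, 18% and 26% of lesions are discordant at the three error levels, and class differences stay at 0.09 to 0.10. Discordance alone does not bias.
- Any shift with slope 0: differences stay at about 0.10. Both conditions are needed.
- Shift 1 mm, slope 0.3: differences fall to 0.07 to 0.09; overall about 0.08. Scale check at the median: 0.3 × log2(16/15) = 0.028.
- Shift 2 mm, slope 0.3: 17%, 23% and 29% discordant; differences fall to 0.04 to 0.08; overall about 0.06. Scale check: 0.3 × log2(17/15) = 0.054.
- One common class per lesion from the mean of two pre-contrast diameters, shift 2 mm: no discordance, and 0.10 recovered in every class.

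**The code.** The MODEL statement has agent and size class as main effects only, while LSMEANS and ESTIMATE ask for `GBCA*class_sized`. A term absent from MODEL cannot be requested there. As written, the size-specific differences cannot be produced. The class-specific figures above describe the evident intention, with the term included.

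**The case against.** The strongest reply is that the SAP is silent rather than wrong. It says only that size is added as a co-factor. A pre-contrast diameter or one value per tracked lesion would fit the text equally well, and lesion tracking (Protocol 8.4.9) supplies the correspondence table needed for either. This stands. A reader might infer that the SAP prescribes agent-specific diameters; it does not, and the defect is an undefined class variable. Nor is the recording rule in Protocol 7.2.6 at fault: it says that each lesion is recorded on its own, and the reading per image set comes from Table 2.

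A reader might also infer that the size-specific results are biased. The documents do not support that. Bias needs an agent effect on measured diameter and a size-dependent score, and neither is quantified.

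The loss of pairing should not be overstated either. Compound symmetry on the lesion keeps the within-lesion correlation even when a covariate differs between the two rows, and the analysis already includes non-matching lesions by design.

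Finally, SAP 4 lists this as a supplemental secondary analysis, and the same lesion-level comparison without size is planned (Table 14.2.2.11), so readers can see whether adjustment moves the estimate. That limits the importance of the point. It does not remove the need to define the variable, because choosing among several possible diameters after unblinding would be a post hoc choice.

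**Conclusion.** The point holds in a limited form, and its severity is minor. The size class is undefined, its most natural implementation adjusts for a post-injection outcome, and that can bias the size-adjusted and size-specific agent differences.

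Under the assumptions of simulation A, 10 to 20% of matched lesions are discordant, and the bias is a few hundredths of a point against the agent with the larger diameters. With no diameter shift there is none. Simulation B gives the same mechanism, with discordance of 9 to 29%. Direction and size in this trial are unknown, because every driving input is assumed.

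It would be tempting to set these values against the 0.35 non-inferiority margin. That margin belongs to the patient-level primary analysis, and no margin or success rule attaches to the size analysis. Neither primary objective uses size class, so neither is affected.

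The missing `GBCA*class_sized` term is a separate fault in the same code block. It is certain and does not depend on any assumption.

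**What to change.** In the lesion-size analysis of SAP 5.6.2:

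1. Derive one size class per lesion and reader, identical on both agents' rows. It could come from the mean of the two Paired diameters, or from the pre-contrast diameters where the lesion is seen on them. The second avoids post-injection information but needs a rule for lesions not visible before contrast.
2. Use that class in the model, in the size-specific estimates and in the descriptive Table 14.2.2.17.
3. Add `GBCA*class_sized` to the MODEL statement so that the requested LSMEANS and ESTIMATE results exist.
4. State how non-matching lesions are classed. With Paired diameters they have only one agent's reading, so a small dependence on agent remains for them. Report the matched-lesion result alongside.

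The cost is a sentence or two in the SAP, one derived variable, one model term and one extra set of matched-lesion results. No new data are needed. The class should be fixed before the blind is broken.

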8 TRIAL SCHEDULE AND PROCEDURES

The schedule of time and events to be performed is given in [Table 1](#).

8.1 Trial Schedule

8.1.1 *Screening Visit – Visit 1 – Day (- 7) to Day 0*

During this visit, the following tasks or assessments will be performed:

- Written informed consent will be obtained from the patient as described in [Section 13.3](#);
- The patient will be attributed an Identification Number (see [section 4.3](#));
- Checking of all eligibility criteria;
- Recording of demographic data (sex, self-reported race/ethnic data, height, age);
- Documentation of relevant medical history/current medical condition present before signing the informed consent including the disease justifying the MRI;
- Recording of patient intolerance history related to contrast agent: if previous intolerance to contrast agent, the type of the product should be collected;
- Documentation of previous CT, MRI or other imaging procedures documenting the region planned to be imaged dated less than 12 months prior to trial MR;
- A routine physical examination (performed by a physician) including the examination of general appearance, skin, neck (including thyroid), eyes, ears, nose, throat, lungs, heart, abdomen, back, lymph nodes, extremities, vascular and neurological; Information indicating the global assessment (normal or abnormal (specify)) of the physical examination should be recorded on source documentation;
- Review and recording of concomitant treatments;
- A urine pregnancy test should be performed for all women of childbearing potential and must be negative.
- IWRS connection for recording the patient screening visit and to ensure an appropriate representation of the different body regions. This means that the patient's inclusion may be refused due to the body region planned to be imaged.
- First trial MRI visit and examination needs to be scheduled within 7 days (or can be performed on the same day if all the inclusion/non-inclusion criteria are met).

8.1.2 *Imaging/Randomization Visit – 1st MRI – Visit 2 – Day 0*

During this visit, the following assessments or tasks will be performed:

Procedures to be performed prior to MRI examination:

- Checking of all the eligibility criteria;
- Any changes in concomitant treatments / procedures / therapeutic measures since the last visit will be documented;
- Measurement of vital signs (systolic and diastolic blood pressure (BP) and pulse Rate (PR)) and weight;

- A urine pregnancy test will be performed for female patient of childbearing potential and must be negative (test done at V1 will not be repeated at V2 if V1 done one day prior to V2. If V1 and V2 are done on the same day, one pregnancy test should be performed prior to patient randomization);
- Blood sample collection for local dosage of serum creatinine and evaluation of eGFR (results should be available prior to patient randomization to check eligibility criteria. eGFR value should be ≥ 30 mL/min/1.73 m² prior to the first MRI); the same local methods of serum creatinine dosage and eGFR calculation should be used throughout the trial for a same patient;
- Blood samples will be collected according to central laboratory manual;
- Assessment of AEs will be documented;
- IWRS connection will be done to randomize the patient, to obtain the IMP box number, to calculate the volume of IMP to be administered based on the body weight and to record the date of the visit.

Unenhanced and contrast-enhanced MRI examinations:

- Unenhanced and contrast-enhanced MRI will be performed according to the required sequences specified in [Section 8.2.2](#)).

The appropriate dose/volume of gadopiclenol and gadobutrol will be administered by IV as a bolus using preferably a power injector in a peripheral vein of the antecubital region (recommended). IMP injection will be followed by a saline flush injection.

The following information will be documented in the source document and reported on clinical eCRF pages: date and time of contrast agent injection, location of injection site, actual volume administered (documentation of difference from theoretical volume), actual injection rate, overdose (if any), number of vials dispensed, number of IMP injected, injection method (power injector or manual), injection of saline flush (yes/no).

The start time of contrast injection will be recorded.

Procedures to be followed after MRI examination:

The patient will stay at the trial site for 60 ± 15 min after the MRI examination is completed and the following procedures will be performed:

- Use/change of concomitant treatments during the visit will be documented;
- Vital signs (systolic and diastolic BP and PR) will be obtained 60 minutes ± 15 minutes after the injection of contrast agent.
- Injection-site tolerance (pain, eruption, extravasation, inflammation, or other) will be assessed during the injection and 60 ± 15 minutes after the injection of contrast agent; In case of pain, the patient will have to complete a Numeric Pain intensity Scale to indicate the pain intensity. Any sign of local intolerance will be reported as AE in the corresponding clinical eCRF page.
- Assessment of AEs will be documented;
- Evaluation of the potential impact of contrast-enhanced MRI on patient treatment plan;
- Safety follow-up visit (Visit 3) needs to be scheduled 1 day post contrast agent injection;

 CONFIDENTIAL	Protocol No. GDX-44-011 Version No. 3.0 (including amendment 2) June 30, 2020	Page 46 / 82
---	---	--------------

- Scheduling of the second MRI examination (visit 4) between 2 days and 14 days post visit 2.

8.1.3 *Safety Visit – Visit 3 – 1 day post visit 2*

During this visit, the following assessments or tasks will be performed:

- Use/change of concomitant treatments / procedures / therapeutic measures will be documented;
- Blood sample collection for local dosage of serum creatinine and evaluation of eGFR; The same local methods of serum creatinine dosage and eGFR calculation should be used throughout the trial for a same patient;
- Blood samples will be collected according to central laboratory manual;
- Vital Signs (systolic and diastolic BP, PR) should be recorded;
- Injection-site tolerance is to be evaluated; In case of pain, the patient will have to complete a Numeric Pain intensity scale to indicate the pain intensity. Any sign of local intolerance will be reported as AE in the corresponding clinical eCRF page.
- Assessment of local serum creatinine results as per ESUR guidelines (see [section 7.2.11](#))
- Assessment of AEs will be documented;
- IWRS connection to record the trial visit;
- Remind the date of visit 4 to the patient.

8.1.4 *Imaging Visit – Visit 4– 2nd MRI – 2 days up to 14 days post V2*

Procedures to be performed prior to MRI examination:

- Checking of certain non-inclusion criteria (see [section 4.2](#));
- Measurement of vital signs (systolic and diastolic BP and PR) and weight;
- Any changes in concomitant treatments / procedures / therapeutic measures since the last visit will be documented;
- A urine pregnancy test will be performed for female patient of childbearing potential prior to the trial MRI and must be negative;
- Blood sample collection for serum creatinine dosage and verification that the local eGFR value is ≥ 30 mL/min/1.73 m²; The same local methods of serum creatinine dosage and eGFR calculation should be used throughout the trial for a same patient;
- Blood samples will be collected according to central laboratory manual;
- Assessment of local serum creatinine results as per ESUR guidelines (see [section 7.2.11](#))
- Assessment of AEs will be documented;

- IWRS connection will be done to obtain the IMP box number, to calculate the volume of IMP to be administered based on the body weight and to record the date of the visit;

Unenhanced and contrast-enhanced MRI examinations:

- Unenhanced and contrast-enhanced MRI will be performed according to the required sequences specified in [Section 8.2.2](#).

The appropriate dose/volume of gadopiclenol and gadobutrol will be administered by IV as a bolus using preferably a power injector in a peripheral vein of the antecubital region (recommended). IMP injection will be followed by a 0.9% saline flush injection.

The following information will be documented in the source document and reported on clinical eCRF pages: contrast agent injection date and time, location of injection site, actual volume administered (documentation of difference with theoretical volume), actual injection rate, overdose (if any), number of vials dispensed, number of IMP injected, injection method (power injector or manual), injection of saline flush (yes/no).

The start time of contrast injection will be recorded.

Procedures to be followed after MRI examination:

The patient will stay at the trial site for 60 ± 15 min after the MRI examination is completed and the following procedures will be performed:

- Use/change of concomitant treatments during the visit will be documented;
- Vital signs (systolic and diastolic BP and PR) will be obtained 60 minutes ± 15 minutes after the injection of contrast agent.
- Injection-site tolerance (pain, eruption, extravasation, inflammation, or other) will be assessed during the injection and 60 minutes ± 15 minutes after the injection of contrast agent; In case of pain, the patient will have to complete a Numeric Pain intensity scale to indicate the pain intensity. Any sign of local intolerance will be reported as AE in the corresponding clinical eCRF page.
- Assessment of AEs will be documented;
- Evaluation of the potential impact of IMP-enhanced MRI on patient treatment plan;
- Safety follow-up visit (Visit 5) needs to be scheduled 1 day post contrast agent injection;

8.1.5 Safety Visit – Visit 5 – 1 day post Visit 4

During this visit, the following assessments or tasks will be performed:

- Use/change of concomitant treatments / procedures / therapeutic measures will be documented;
- Blood sample collection for local dosage of serum creatinine and evaluation of eGFR. The same local methods of serum creatinine dosage and eGFR calculation should be used throughout the trial for a same patient;
- Assessment of local serum creatinine results as per ESUR guidelines (see [section 7.2.11](#))
- Blood samples will be collected according to central laboratory manual;

 CONFIDENTIAL	Protocol No. GDX-44-011 Version No. 3.0 (including amendment 2) June 30, 2020	Page 48 / 82
--	---	--------------

- Vital Signs (systolic and diastolic BP, PR) should be recorded;
- Injection-site tolerance is to be evaluated; In case of pain, the patient will have to complete a Numeric Pain intensity scale to indicate the pain intensity. Any sign of local intolerance will be reported as AE in the corresponding clinical eCRF page.
- Assessment of AEs will be documented (any AE not recovered should be followed up (see [section 9.1.2](#));
- IWRS connection to record the trial visit;

During the course of the trial, if a patient is screen failed or is prematurely discontinued (see [section 14.3.2](#)), the new patient status should be recorded in the IWRS and in the clinical eCRF.

